8.4 General Statistical Methods

The Sponsor's Biostatistics and Data Management group will be responsible for data management and statistical analysis of this study. All statistical analyses will be performed using SAS for Windows (Version 9.4 or higher). Patient data listings and tabular presentations of results will be provided. Further details of the criteria and conduct of the statistical analyses will be included in the SAP for this study.

8.5 Efficacy Analysis:

The primary efficacy variable ORR is the proportion of patients with confirmed Complete Response (CR) and Partial Response (PR) recorded from the start of the first dose of poziotinib to the end of study and will be analyzed descriptively along with the 95% CI for each cohort. The determination of ORR will be based upon an assessment of the local radiological review by the respective Principal Investigator using RECIST version 1.1 and/or RANO criteria (for GBM). Confirmatory assessments must be completed by the Investigator 4 weeks \pm 3 days after the first assessment of CR or PR and only confirmed CR/PR can be deemed as CR/PR.

The secondary endpoints are DCR and DoR, DCR is the proportion of patients with best response of CR, PR, and Stable Disease (SD) from the first dose of poziotinib to the end of study; and DoR is the time from the date that measurement criteria are first met for CR or PR (whichever status is recorded first) until the first subsequent date that progressive disease or death is documented.

Exploratory endpoints are OS and PFS. OS is the time from the treatment start date to the date of death during the study and PFS is the time from the treatment start date to the date of documented disease progression or death during the study.

DCR, DoR, OS, and PFS will be analyzed using descriptive statistics, for each cohort, and with 95% CI for DCR and Kaplan-Meier plot for DoR, OS, and PFS.

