8 STATISTICAL PLAN

A Statistical Analysis Plan (SAP) will be provided before data base lock.

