8.1 Sample Size

The statistical analysis of each cohort will be performed separately. A total of 30 patients in each cohort will be enrolled using Simon's two-stage design. The optimal two-stage design to test the null hypothesis that $p \leq 0.050$ versus the alternative that $p \geq 0.250$ has an expected sample size of 16.76 and a probability of early termination of 0.630. If the drug is not effective, there is a 0.049 probability of concluding that it is (the target for this value was 0.050). If the drug is effective, there is a 0.098 probability of concluding that it is not (the target for this value was 0.100). For each cohort, 9 patients will be evaluated in the first stage; the cohort will be terminated if 0 respond. If the cohort goes on to the second stage, a total of 30 patients will be studied. If the total number responding is less than or equal to 3, the cohort is closed.

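### Does the 95% CI for ORR in section 8.5 contradict the two-stage success rule when a cohort finishes at exactly 4/30?

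*Combined protocol and SAP*

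**What the plan says.** Section 8.1, repeated in the Synopsis, sets up a Simon optimal two-stage design in each cohort, with a null ORR of at most 5% against an alternative of at least 25%. On the interim look it says "9 patients will be evaluated in the first stage; the cohort will be terminated if 0 respond". On the final look it says "If the total number responding is less than or equal to 3, the cohort is closed". A cohort therefore passes with at least 1 responder in 9 and at least 4 in 30. The stated error is that "If the drug is not effective, there is a 0.049 probability of concluding that it is". Sidedness is not written, but the hypotheses point one way.

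Section 8.5 and the Synopsis treat the same endpoint differently: ORR "will be analyzed descriptively along with the 95% CI for each cohort". No interval method is named, no p-value is planned, and no sentence relates the interval to the 5% null. Section 8 adds: "A Statistical Analysis Plan (SAP) will be provided before data base lock". Section 8.4 also leaves further analysis detail to that document.

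**The concern.** The plan defines success for the primary endpoint by a one-sided test at about 5% and then reports that endpoint with an interval that is conventionally two-sided at 95%. At the smallest passing count, 4/30, the common exact interval reaches below 5%, while another standard interval does not. A cohort could be declared a success and published with an interval that seems to say the null was not excluded.

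The method is also open until database lock. The trial is open-label, response is read locally, and the sponsor's own group does the analysis. In principle the method could be chosen once the responses are known. What is at stake is how a borderline pass reads in a report. The decision to continue or close a cohort is not affected.

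**Working it through.** **Inputs.** From section 8.1: null rate 0.05, alternative 0.25, first stage 9 patients (stop at 0), total 30 (fail at 3 or fewer). From section 8.5: a 95% CI, taken as two-sided.

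**Reproducing the plan's figures.**
- Probability of early termination under the null: 0.95^9 = 0.630.
- Expected sample size: 9 + (1 − 0.6302) × 21 = 16.76 to 16.77 by rounding (unrounded 16.765; the plan has 16.76).
- Type I error: sum over x = 1 to 9 of P(Bin(9, 0.05) = x) × P(Bin(21, 0.05) ≥ 4 − x). The terms for x = 1, 2 and 3 are 0.2985 × 0.0849 = 0.0254, 0.0629 × 0.2830 = 0.0178 and 0.0077 × 0.6594 = 0.0051. For x ≥ 4 the contribution is 0.0006. The total is 0.0489 (plan: 0.049).
- Type II error: 1 − 0.9019 = 0.0981 (plan: 0.098).

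The design is correct as stated.

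**The intervals near the cut.** Entries are lower limits; the rule passes from 4/30 upward.

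| Responders | Two-stage p | Clopper-Pearson 95% | Wilson 95% | Wald 95% | Stage-wise, one-sided 95% |
|---|---|---|---|---|---|
| 3/30 | 0.134 | 2.1% | 3.5% | 0.0% | 3.2% |
| 4/30 | 0.0489 | 3.8% | 5.3% | 1.2% | 5.04% |
| 5/30 | 0.0136 | 5.6% | 7.3% | 3.3% | 7.1% |

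At 4/30 the full 95% intervals are 3.8% to 30.7% (Clopper-Pearson), 5.3% to 29.7% (Wilson) and 1.2% to 25.5% (Wald). With Clopper-Pearson the apparent conflict exists at 4/30 only. With Wald it extends to 5/30 and is gone at 6/30 (lower limit 5.7%).

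**Where the mismatch comes from.** An exact 95% interval excludes 5% only if the upper-tail probability at 5% is at most 0.025. The rule needs it to be at most 0.05. The two-stage p of 0.0489 lies between these. A 95% interval that fully respects the two-stage design still has a lower limit of 4.0% at 4/30, so the confidence level is the main cause.

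Ignoring the interim stop adds a smaller part. The single-stage tail P(Bin(30, 0.05) ≥ 4) is 0.0608. It exceeds 0.0489 by 0.6302 × 0.0189 = 0.0119, the chance of 0/9 followed by at least 4 of 21, a path the design does not allow.

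**Validity of the ordinary interval.** Counting over all outcomes of the two-stage design, the Clopper-Pearson 95% interval covers the true rate 97.3% to 99.2% of the time for true ORR of 5% to 25%. It is conservative, not misleading.

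**How often 4/30 occurs.**

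| True ORR | P(pass at exactly 4/30) | P(pass) | Share of passes | At least one of five cohorts |
|---|---|---|---|---|
| 5% | 3.5% | 4.9% | 72% | 16% |
| 10% | 13.8% | 29.4% | 47% | 53% |
| 15% | 15.9% | 58.8% | 27% | 58% |
| 20% | 10.4% | 79.3% | 13% | 42% |
| 25% | 4.7% | 90.2% | 5% | 21% |

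The last column is 1 − (1 − P)^5 and assumes five independent cohorts with the same true ORR. The protocol does not make that assumption.

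**The case for a change.** The best case for a change is that section 8.1 speaks of concluding that the drug is effective, so an inference is planned, yet section 8.5 never reports it. A reader shown 13.3% with limits of 3.8% and 30.7% might reasonably think 5% was not ruled out. An interval matched to the test exists: the stage-wise one-sided 95% lower limit (the lower end of a 90% interval) is 3.2%, 5.04% and 7.1% at 3, 4 and 5 of 30, so it agrees with the rule on both sides of the cut. An ordinary exact 90% interval would not do this, since its lower limit at 4/30 is 4.7%. Settling the method early would cost a few sentences and would close off a choice made with responses in view.

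All of that arithmetic stands, and so does the observation that the method is unnamed. The inference that the plan needs repair does not stand. A matched interval would be reported beside the 95% interval, and if that is Clopper-Pearson it would still contain 5% at 4/30. The extra p-value and interval are a reporting preference. Saying that the count governs would largely restate sections 8.1 and 8.5. A late, result-driven choice of method is possible, but nothing in the protocol suggests it, and it could not move a cohort across the success line.

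**Conclusion.** No change is needed. The responder count is the sole decision rule, its stated error rates are reproduced, and the 95% CI is presented as description. A one-sided 5% test and a two-sided 95% interval can differ near the cut without either being wrong. Here they differ at one outcome with Clopper-Pearson, 4/30, which has probability 4.7% per cohort if the true ORR is 25% and at most 15.9% at the five rates examined. No decision, error rate or procedure depends on it.

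The missing method name is a gap that an analyst would fill sensibly in the promised SAP. The usual exact interval is valid and conservative in this design.

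The conclusion rests on three readings: the CI is two-sided, the rule is one-sided, and the analysed numbers are exactly 9 and 30. Efficacy is analysed in the Evaluable Population, so a cohort could end with a different denominator and the limits above would need recalculating. That would not make the interval a decision criterion.

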This study includes a two-stage design in each cohort separately. The first-stage of each cohort will enroll 9 patients. Details of the two-stage design are provided in the statistical section. A cohort will enroll patients into the second-stage if the required responses are observed in 9 patients in the first-stage for each cohort.

Dosing Regimen

The starting dose of poziotinib is 8 mg, twice per day (BID). Poziotinib will be self-administered by the patient orally, with food and a glass of water, at approximately the same time(s) each day during each 28-day cycle.

The first dose should be taken in the morning and the second dose should be taken approximately 8 to 12 hours later. If a dose is missed, it should be taken once remembered or with the next dose if on the same day.

All patients will be given loperamide for daily use, starting from the first day of the study (4 mg two to three times a day or according to the treating physician's instruction). Poziotinib dose modifications are allowed based on the guidelines provided (**Table 2**).

The Screening period (Day -30 to Day 1) lasts up to 30 days prior to Cycle 1, Day 1. Patients must provide written Informed Consent prior to undergoing any study procedure. Patients must meet all Inclusion/Exclusion Criteria in order to participate in the study. Each treatment cycle is 28 calendar days in duration, regardless of dosing interruptions. Tumor assessments are scheduled at Baseline/pre-dose, Week 4, Week 8 and every 8 weeks thereafter. In the event of a response (PR or CR), a confirmatory scan may be performed 4 weeks from the initial response. Pre-dose tumor assessments must be within 14 days prior to Cycle 1, Day 1 (Baseline assessments may be used if obtained within 14 days prior to Cycle 1, Day 1).

The treatment period for all patients will be from the time of the first dose of poziotinib to the first occurrence of disease progression, intolerable adverse events, the start of a new anti-cancer treatment, withdrawal of consent or death.

Following radiologic disease progression, the patient may continue to receive poziotinib in an Extension Study (SPI-POZ-501) only if the following criteria are met: absence of signs and symptoms indicating clinical deterioration due to progression of disease or drug toxicity and absence of decline in ECOG performance status, or the investigator and medical monitor agree that the patient continues to derive clinical benefit despite progressive disease.

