3 INVESTIGATIONAL PLAN

3.1 Study Design and Treatment Plan

This is a Phase 2 multicenter, open-label study to evaluate the efficacy and safety of poziotinib in patients with eligible EGFR or HER2 mutation-positive malignant solid tumors.

The study is a basket trial with five patient cohorts. The primary analysis will be conducted for each cohort separately. The five patient cohorts are:

- **Cohort 1:** Patients that have HER2-positive or HER2-negative breast cancer with HER2 activating mutations (see Table A in Section 4.1) (N=30) (See Inclusion Criteria #4)
- **Cohort 2:** Patients that have colorectal cancer with HER2 activating mutations (see Table A in Section 4.1) (N=30)

- **Cohort 3:** Patients that have solid tumors (except NSCLC, breast cancer, or colorectal cancer) with HER2 activating mutations (see **Table A** in Section 4.1) (N=30)
- **Cohort 4:** Patients that have GBM with EGFR activating mutations (see **Table A** in Section 4.1) (N=30)
- **Cohort 5:** Patients that have solid tumors (except NSCLC or GBM) with EGFR activating mutations (see **Table A** in Section 4.1) (N=30)

This study includes a two-stage design in each cohort separately. The first-stage of each cohort will enroll 9 patients. Details of the two-stage design are provided in the statistical section. A cohort will enroll patients into the second-stage if the required responses are observed in 9 patients in the first-stage for each cohort.

The **Screening** period (Day -30 to Day 1) lasts up to 30 days prior to Cycle 1, Day 1. Patients must provide written Informed Consent prior to undergoing any study procedure. Patients must meet all Inclusion/Exclusion Criteria to participate in the study. Each treatment cycle is 28 calendar days in duration, regardless of dosing interruptions. Tumor assessments are scheduled at Baseline/pre-dose, Week 4, Week 8 and every 8 weeks thereafter. In the event of a response (PR or CR), a confirmatory scan may be performed 4 weeks from the initial response. Pre-dose tumor assessments must be within 14 days prior to Cycle 1, Day 1 (Baseline assessments may be used if obtained within 14 days prior to Cycle 1, Day 1).

The treatment period for all patients will be from the time of the first dose of poziotinib to the first occurrence of disease progression, intolerable adverse events, the start of a new anti-cancer treatment, or death.

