5.3.6 Treatment Period – Cycle 2, Day 8 (± 1 Day)

- Complete blood count with 5-part differential and platelets
- Adverse event assessment using NCI CTCAE, Version 5.0; a telephone call to patient for the follow up of AEs between Days 3 to 8
- Patient Diary review
- Concomitant medications review

5.3.7 Treatment Period – Cycle 3+, Day 1

- Weight
- Physical examination
- Vital Signs
- ECOG Assessment
- Urine pregnancy test in women of childbearing potential
- Tumor assessment: either CT, PET/CT, or MRI for non-brain organs and brain MRI (unless the patient has documented disease progression or has undergone a tumor assessment with the previous 8 weeks; the same imaging acquisition method as the baseline should be used)
- Complete blood count with 5-part differential
- Serum chemistry
- Plasma sample for biomarker analysis
- Dispense poziotinib and loperamide
- Adverse event assessment using NCI CTCAE, Version 5.0
- Dispense and Collect Patient Diary
- Concomitant medications review

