5.3.8 End-of-Treatment Visit (30 [± 5] Days After Last Dose of Study Treatment)

The **End-of-Treatment Visit** is required 30 (± 5) days after the last dose of poziotinib is administered. The following assessments are to be performed at this visit:

- Height and Weight
- Physical examination
- Vital signs

- ECOG Performance Status assessment
- Urine pregnancy test in women of childbearing potential
- Tumor assessment (either CT, PET/CT, or MRI for non-brain organs and brain MRI (unless the patient has documented disease progression or has undergone a tumor assessment within the previous 8 weeks; same imaging acquisition method as the baseline should be used)
- CBC with 5-part differential and platelets
- Serum chemistry
- Newly biopsied tumor tissue taken from patients who progress for biomarker analysis (optional, but encouraged)
- Plasma sample for biomarker analysis if the patient progresses (optional)
- Adverse event assessment using NCI CTCAE, Version 5.0
- Patient Diary Collection
- Concomitant medications review

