5.4.9 Tumor Assessment

Tumor assessment for study patient's eligibility must be performed by Investigators using computed tomography (CT), positron emission tomography (PET)/CT, or magnetic resonance imaging (MRI) for non-brain organs and MRI for brain at **Screening** up to 30 days prior to **Cycle 1, Day 1**. Imaging studies performed prior to the signing of Informed Consent as part of the site's routine standard of practice are allowed at the discretion of the Sponsor as the Screening assessment. Brain MRI must be performed to assess the brain metastasis status at the screening per eligibility criteria. This information is to be discussed with the Sponsor's Medical Monitor before the patient is enrolled in the study. **Baseline** tumor assessment will be performed within 2 weeks prior to, or on **Cycle 1, Day 1**. Post-Baseline tumor assessments must be performed at **Cycle 2 Day 1**, at **Cycle 3 Day 1**, and every 8 weeks thereafter until patient discontinuation.

Each subsequent tumor assessment must use the same radiologic technique as in Baseline, either CT, PET/CT, or MRI. Tumor assessments will be made according to RECIST, version 1.1 [14] using appropriate radiologic imaging or other techniques. For radiographic assessment, CT, PET/CT, or MRI must be performed at every assessment.

In Cohort 4, tumor assessments will be made using appropriate radiologic imaging techniques as per RECIST 1.1 and/or the RANO criteria [15].

Measurable and non-measurable lesions should be documented appropriately.

Tumor assessment is based on the study investigator's assessment with local radiology review and report according to the RECIST 1.1 and/or RANO (for **Cohort 4**) criteria for response evaluation.

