b) Patients will be contacted by telephone on Days 3-8 and on Day 22 for assessment of adverse events.

c) An **End-of-Treatment Visit** will be performed 30 (±5) days after the last dose of poziotinib. An End of Study page will be recorded at that time.

d) A complete physical examination is required at **Screening, Day 1** of each Cycle, at Days 8 and 15 of Cycle 1, and at the **End-of-Treatment Visit**. Symptom-directed exams if clinically indicated are required at other visits.

- e) Pregnancy test (β -HCG) in women of child-bearing potential. Blood pregnancy test is required at **Screening**. Urine pregnancy test is required on Day 1 of each Cycle starting from **Cycle 2** and at **Cycle 1, Day 1**, if Screening pregnancy test was more than 7 days prior to **Day 1**. Urine pregnancy test also required at **End-of-Treatment Visit**.
- f) The **Screening** tumor assessment for patient eligibility will be based on scans performed within 30 days before the patient signed the ICF. Either CT, PET/CT, or MRI scans should be performed for non-brain organs and brain MRI scans should be performed locally per standard of care before the patient signed the ICF. **Baseline** tumor assessment (CT, PET/CT or MRI for non-brain and brain MRI) will be performed within 14 days prior to **Cycle 1, Day 1** and additional assessments will be made at 4 weeks (**Cycle 2, Day 1** [up to **Cycle 2, Day 7**]), at 8 weeks (**Cycle 3, Day 1** [up to **Cycle 3, Day 7**, with at least 28 days from previous tumor assessment]), and then every 8 weeks (± 7 days) thereafter until disease progression, death, intolerable adverse events (AEs), or other protocol-specified reasons for patient withdrawal.
- g) Tumor histopathology report (from local pathologist) and molecular test report for mutation diagnosis.
- h) Complete blood count (CBC), including white blood cells with 5-part differential, hemoglobin, and platelets, is to be obtained within 7 days prior to poziotinib administration on **Day 1** of each cycle, at which time, the patient's absolute neutrophil count $\geq 1.0 \times 10^9/L$ and platelet count $\geq 75 \times 10^9/L$ before administering the next dose of poziotinib. In addition, a CBC is to be performed on **Day 8** of **Cycles 1 and 2**.
- i) Blood for chemistry is to be collected within 7 days prior to poziotinib administration on **Day 1** of each Cycle.

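### Section 8.5 counts a response only if confirmed 4 weeks ±3 days later, but that scan is optional in the Synopsis and Section 3.1 and absent from the schedule, so a durable response first seen at Week 8 or later can go uncounted

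*Combined protocol and SAP*

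**What the plan says.** Section 8.5 defines ORR as the proportion of patients with confirmed CR or PR and sets the rule: "Confirmatory assessments must be completed by the Investigator 4 weeks", ±3 days, after the first CR or PR. It adds that "only confirmed CR/PR can be deemed as CR/PR".

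Section 3.1 treats the same scan as optional: "In the event of a response (PR or CR), a confirmatory scan may be performed 4 weeks from the initial response". The Synopsis (Study Design and Methodology) uses the same optional wording. Neither gives a window.

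The operational text contains no confirmatory scan. Footnote f of the schedule (Synopsis and Appendix 1) lists Week 4, Week 8 ("with at least 28 days from previous tumor assessment") and then every 8 weeks ±7 days. Section 5.4.9 lists Cycle 2 Day 1, Cycle 3 Day 1 "and every 8 weeks thereafter until patient discontinuation". Section 5.3.7 waives the Cycle 3+ Day 1 scan if the patient "has undergone a tumor assessment with the previous 8 weeks" (sic), and Section 5.3.8 waives the End-of-Treatment scan if the patient "has undergone a tumor assessment within the previous 8 weeks". Neither waiver makes an exception for a response awaiting confirmation.

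Section 8.1 uses the response count twice in each cohort: stop at 0 of 9, and close at 3 or fewer of 30.

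**The concern.** The primary endpoint has two incompatible operating rules. A site working from Section 3.1, the visit lists and Appendix 1 can follow the calendar, omit the optional scan, and have a patient whose PR persists on every later scan but who, on a literal reading of 8.5, is not a responder. The protocol does not say whether a confirmation outside the 4-week window is accepted.

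The cut-offs are small, so a single uncounted responder can decide a cohort: one confirmed response among nine keeps it open, and the final decision turns on three versus four. Any loss biases ORR downward and makes it likelier that an active cohort is closed.

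**Working it through.** **1. Which routine scans fall in the confirmation window?** The window is 28 ± 3 = 25–31 days after first response. Scan days are counted from first dose, using footnote f: Week 4 = 28 to 34; Week 8 = 56 to 62, at least 28 days after the previous scan; Week 16 = 112 ± 7 = 105 to 119; Week 24 = 168 ± 7 = 161 to 175.

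| First response seen at | Next routine scan | Gap (days) | In 25–31? |
|---|---|---|---|
| Week 4 | Week 8 | 28 to 62 − 28 = 34 | Yes for 28–31; no for 32–34 |
| Week 8 | Week 16 | 105 − 62 = 43 to 119 − 56 = 63 | Never |
| Week 16 or later | 8 weeks later | 161 − 119 = 42 to 175 − 105 = 70 | Never |

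Footnote a allows cycles to vary by ±3 days. If both intervening cycles ran 3 days short, the minimum gaps would be 43 − 6 = 37 and 42 − 6 = 36 days, still beyond 31.

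**2. The waivers.** Read literally, Section 5.3.7 lets a Week 4 scan cancel the Week 8 scan. That is the only routine on-treatment scan able to confirm a response, and Section 5.4.9 requires it. The End-of-Treatment visit is 30 ± 5 days after the last dose, so its scan could fall in the window for a patient who stops soon after a first response; Section 5.3.8 waives it in that case.

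**3. Reproduce the design (Section 8.1: stop at 0/9; fail at ≤3/30; p = 0.05 versus 0.25).**

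- Early termination: PET(p) = (1 − p)^9. At 0.05: 0.95^9 = 0.630. At 0.25: 0.75^9 = 0.075.
- Expected N at p = 0.05: 9 + 21 × (1 − 0.6302) = 16.76.
- Probability of success: Σ over x = 1 to 9 of C(9,x) p^x (1 − p)^(9−x) × P(Bin(21, p) ≥ 4 − x). At 0.05 this is 0.0489; at 0.25 it is 0.9019, so type II error is 0.098.

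All four stated figures (16.76, 0.630, 0.049, 0.098) are reproduced.

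**4. Sensitivity to uncounted responses.** The documents give no loss rate, so L below is an assumption. A share L of true responses uncounted changes p to p(1 − L), under both the alternative and the null.

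| L (assumed) | 0.25(1 − L) | Stop at 0/9 | Power | 0.05(1 − L) | Alpha |
|---|---|---|---|---|---|
| 0 | 0.250 | 0.075 | 0.902 | 0.050 | 0.049 |
| 10% | 0.225 | 0.101 | 0.857 | 0.045 | 0.035 |
| 20% | 0.200 | 0.134 | 0.793 | 0.040 | 0.024 |
| 30% | 0.175 | 0.177 | 0.704 | 0.035 | 0.016 |

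Power falls to 0.80 at a loss of about 19% (p = 0.2024).

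One way to reach such losses, again assumed: half of responses are first seen at Week 8 or later, and 25% or 50% of those get no extra scan. Then L = 0.5 × 0.25 = 12.5% (power 0.843, stop at 0/9 0.108) or 0.5 × 0.5 = 25% (power 0.752, stop at 0/9 0.154).

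**The case against.** The strongest reply is that the protocol already requires the scan. Section 8.5 places the duty on the investigator, Section 9.3 holds the Principal Investigator to the protocol's procedures, and the Synopsis also defines ORR by confirmed response. The permissive wording in Section 3.1 could simply authorise an off-calendar scan. The schedule grid marks tumor assessment at Cycle 3+ Day 1 with a ±3-day visit window, which would suit a confirmatory scan. Section 8.5 does not expressly void a late confirmation, and Section 8.4 leaves further criteria to the SAP. Read literally, the Section 5.3.7 waiver would cancel nearly every on-time scan, so it was probably meant only to avoid scanning every cycle. The loss rate is assumed, 0.25 may already be a confirmed rate, and Section 8.1 speaks only of responding. The error cannot create false positives, and accepting a later confirmation alters the endpoint definition in an open-label, locally read study.

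Some of this stands. The size of the loss is unknown, the design arithmetic is right, the gap limits can shift by a few days, and a site that follows 8.5 loses nothing. The rest does not remove the problem:

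- A duty stated only in the statistical section does not cure contrary wording in the design section and silence in the schedule that sites work from. Footnote f limits the Cycle 3+ mark to 8-weekly scans.
- The SAP is promised only before database lock. It cannot recover a scan never taken or reopen a cohort already stopped at 0/9.
- Because 8.5 says only confirmed responses count as CR or PR, the natural reading is that confirmed responses drive both Section 8.1 decisions.
- A response that persists on a later scan has lasted longer than 8.5 demands, so counting it does not weaken the evidence of durability.

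**Conclusion.** The concern holds, and the text is wrong as written. No scheduled on-treatment scan can confirm, within the Section 8.5 window, a response first seen at Week 8 or later; confirmation then depends on a scan that two sections make optional and the schedule omits. Some Week 4 responses also miss the window, when the Week 8 scan falls 32–34 days later. This follows from the documents' own visit windows.

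The operating consequence is conditional. The stated alpha and power are correct when every response gets its 4-week scan. Assumed losses of 10–30% reduce power from 0.902 to between 0.857 and 0.704. The bias is conservative (alpha falls), so the risk is closing an active cohort. It should be corrected before cohort decisions are taken, because a missing scan cannot be repaired at analysis.

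**What to change.** - Make the confirmatory assessment mandatory in the Synopsis and Section 3.1, matching Section 8.5.
- Add it to the Schedule of Assessments in the Synopsis and Appendix 1, at 4 weeks ±3 days after the first CR or PR. State that the scheduled Week 8 scan serves when it falls in that window, and that otherwise an extra scan is required.
- In Section 8.5, keep the 25-day lower bound and state that, if the required scan is missed or late, a CR or PR that persists on a later scan, including the next scheduled one, counts as confirmed.
- Reconcile the Section 5.3.7 waiver with the Week 8 scan required by Section 5.4.9, and state that the waivers in Sections 5.3.7 and 5.3.8 do not apply while a confirmation is pending.

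The cost is protocol wording and at most one extra scan per responder, which 8.5 already requires. Where the 4-week scan is missed, confirmation, and possibly a stage-1 decision, could come up to 63 − 31 = 32 days (Week 8 responders) or 70 − 31 = 39 days (later responders) after the present day-31 limit.
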